Recently, there has also been interest in maintaining low insufflation pressure during laparoscopic surgery because lower pressures may decrease postoperative pain.¹⁰ It is hypothesized that deep NMB will provide good surgical conditions and minimize postoperative pain at low insufflation pressures of 7 to 10 mmHg, but this theory has not been adequately evaluated, especially in obese patients.

At the present time, there is no conclusive evidence that surgeons need deep NMB for laparoscopic bariatric surgery and even that surgeons can discriminate between moderate and deep NMB.¹¹ The goal of this prospective, randomized, assessor-blinded controlled trial is to test the hypothesis that deep NMB provides optimal surgical conditions during laparoscopic bariatric surgery in the morbidly obese patient. In addition, we will determine if deep NMB allows the surgeon to utilize lower insufflation pressure and decreases postoperative pain requirements after laparoscopic bariatric surgery.

2.3 Study Design:

Study design: prospective, randomized, assessor-blinded controlled trial that will be performed at a single academic hospital. The surgeons, subjects, and individuals performing the postoperative assessments will be blinded to the study group assignment. The anesthesia providers responsible for the clinical care of the patients will be aware of the rocuronium NMB treatment group and NMB and insufflation status throughout the surgical procedure.

2.4 Study Design:

2.5 Study Procedures:

- I. Patient population: this study will enroll 145 adults undergoing elective laparoscopic bariatric surgery. Our aim is to randomize 140 patients and this will allow 5 subjects to drop out of the study after enrollment.
- II. Inclusion criteria:
 - a. Age \geq 18 years
 - b. ASA I-III
 - c. BMI \geq 35
- III. Exclusion criteria:
 - a. Inability to obtain written informed consent
 - b. Pregnancy or breastfeeding
 - c. Allergy to rocuronium, sugammadex, or any anesthetic agents used in the protocol
 - d. Known or suspected neuromuscular disorders
 - e. Significant renal disease with a serum creatinine \geq 2 mg/dl
 - f. Significant liver disease
 - g. A family history of malignant hyperthermia

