- IV. Randomization: On the day of surgery, patients will be randomized to one of four groups: 1. moderate NMB + 10 mm insufflation pressure (IP); 2. moderate NMB + 15 mm IP; 3. deep NMB + 10 mm IP; or 4. deep NMB + 15 mm IP. Randomization will be stratified for the four groups so that obese patients with BMI of 35 to 45 and those with a BMI $>$ 45 are equally distributed between the groups.
- V. Blinding: The surgeon, operating room staff, patients, personnel in the postanesthesia care unit (PACU) as well as the investigators collecting the postoperative data will be blinded to the group allocation. The surgeon will also

be blinded to the initial insufflation pressure. The rocuronium infusions will be prepared in a room away from any of the blinded personnel. The anesthesia providers administering the anesthesia will be aware of the randomization and the dose of rocuronium that the patient is receiving. The TOF watch will be draped so that the surgeons and operating room personnel are unable to observe it during the procedure. The insufflation pressures will also be covered. .

VI. Anesthetic management

a. Monitoring

1. All patients will be monitored with standard monitors including ECG, non-invasive blood pressure, pulse oximetry, esophageal temperature, capnography, and a BIS® depth of anesthesia monitor.
2. Muscle relaxant monitoring – neuromuscular function will be monitored using acceleromyography with the TOF-Watch® SX (Organon Ireland Ltd, a subsidiary of Merck and Co., Inc., Swords, Co. Dublin, Ireland). The TOF tracing will be stabilized after induction of anesthesia (prior to the administration of muscle relaxant drugs) according to the manufacturer's recommended protocol.

b. Anesthetic Technique – all patients will receive a standardized general anesthetic technique and all anesthetic medications (with the exception of sugammadex) will be dosed on the ideal body weight rather than actual weight.

1. Premedication – midazolam, 1-2 mg iv in the holding area
2. Preoxygenation with 100% oxygen for a minimum of 3 minutes
3. Induction – propofol, 2 – 2.5 mg/kg, iv and fentanyl, 2-3 micrograms/kg, iv. Additional propofol or fentanyl may be administered at the discretion of the anesthesia provider
4. Intubation – succinylcholine, 1.5 mg/kg, iv after loss of consciousness to facilitate tracheal intubation

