- b. Fentanyl PCA will be started in the postanesthesia recovery room and continued for the first 24 – 48 hours after surgery.

VIII. Perioperative assessments

- a. Surgeon satisfaction – the primary endpoint is the surgeon's satisfaction with the level of NMB during surgery at the start of the case (the initial score). The satisfaction level will be rated with a five-point ordinal scale ranging from 1 (extremely poor) to 5 (optimal conditions). This scale is outlined in detail in table 1 (page 15) and is adopted from a previously published studies.⁶ For each patient, the first surgeon satisfaction rating during the procedure (prior to any rescue measure) will be the primary outcome measure.
- b. During the laparoscopic procedure, the surgeon will score the surgical working conditions. The first rating will occur when the NMB level is stable at either deep or moderate block (per randomization) and the intra-abdominal pressure is either 10 or 15 mm Hg per a second randomization list. The surgeon will be blinded to the insufflation pressure at this point. If the conditions are rated as extremely poor or poor (surgical rating of 1-2, Table 1), the following steps will be taken in an incremental manner. The surgeon may also request rescue

treatment if the surgical rating scale is 3 (acceptable), but he anticipates deterioration in the surgical condition during the procedure :

1. Increase the insufflation pressure to a maximum of 15 mm Hg –the surgeon will reassess the surgical field after the intra-abdominal pressure is stable at 15 mm Hg for 2-3 minutes. At this point the insufflation pressure will remain at 15 mm Hg for the remainder of the procedure.
2. Additional muscle relaxation – if the surgeon rates the working conditions as 1 (extremely poor) or 2 (poor) after increasing the insufflation pressure to 15 mm Hg, the surgeon may then request additional muscle relaxant. At this point the anesthesia provider will check the level of NMB. If the patient is in the moderate group and has 1 or more twitches, the anesthesia provider will administer a bolus dose of rocuronium, 0.3 mg/kg iv. If the patient has only 0-1 PTC, the anesthesia provider will administer an equal volume of iv saline. The surgeon will rate the surgical working conditions at 2-3 minutes after the additional dose of medication.

- c. Intra-abdominal insufflation pressures and TOF ratio measurements will be recorded every 15 minutes during the procedure.

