- d. Surgeons will be asked to rate their satisfaction with the surgical field every 30 minutes during the procedure.
- e. Perioperative variables will also be recorded including the duration of surgery, time from administration of NMJ reversal (sugammadex) to extubation, time from end of surgery to exit from the OR, time in the PACU, and length of hospital stay.
- f. Postoperative verbal pain levels (0 = no pain to 10 = worst imaginable pain) and opioid requirements will be assessed daily. Patients will also be asked about the presence or absence of shoulder pain.

- g. Postoperative variables including the need for postoperative mechanical ventilation, re-intubation, residual paralysis, pneumonia, infections, and other adverse events during the hospital stay. The need for ICU admission and length of hospital stay will also be collected.

2.6 Study Duration:

The Missouri Bariatric Service at the University of Missouri-Columbia performs over 600 bariatric procedures per year. The Director for this service, [name] [name], is a co-investigator on the study. He has 3 full day operating blocks per week and we estimate that we can easily enroll 15 patients per month.

We estimate that patient enrollment can be completed in 9 months. We will need an additional 3 months after enrollment is complete for data analysis and abstract/manuscript preparation.

Statistical Analysis and Sample Size Justification:

[figure not shown]
Data analysis will be based on an intent-to-treat approach. The primary endpoint will be the first surgeon satisfaction rating measured on a five-point ordinal scale (Table 1). The experimental layout is a randomized two-factor design so the primary analysis will be the two-way Analysis of Variance (ANOVA) with interaction. A statistically significant interaction will be followed by pairwise comparisons to identify and estimate treatment combination differences. The standard ANOVA assumes a normally distributed outcomes with homogeneous variances and so the robustness of the results will be checked against an aligned-rank test for the two-way layout.¹²

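### The plan does not say how many surgeons give the primary rating; if more than one does, the two-way ANOVA has no surgeon term and the interaction test loses precision

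*Combined protocol and SAP*

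**What the plan says.** **Outcome.** Section 2.5, item VIII.a: "The satisfaction level will be rated with a five-point ordinal scale ranging from 1 (extremely poor) to 5 (optimal conditions"), and "the first surgeon satisfaction rating during the procedure (prior to any rescue measure) will be the primary outcome measure". The operating surgeon gives the score.

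**Who rates.** The wording is mixed.
- Plural: section 2.3 states "The surgeons, subjects, and individuals performing the postoperative assessments will be blinded to the study group assignment". Item V of section 2.5 uses both the singular and the plural. Item VIII.d states "Surgeons will be asked to rate their satisfaction with the surgical field every 30 minutes during the procedure".
- Singular: items VIII.a and VIII.b, which define the first rating, speak of one surgeon, for example "but he anticipates deterioration in the surgical condition during the procedure". Section 2.6 bases accrual on the co-investigator who directs the bariatric service: "He has 3 full day operating blocks per week and we estimate that we can easily enroll 15 patients per month".

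No eligibility criterion limits cases to one operator, and the number of raters is given nowhere.

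**Randomization.** Section 2.5, item IV: "Randomization will be stratified for the four groups so that obese patients with BMI of 35 to 45 and those with a BMI" above 45 are equally distributed. Surgeon is not a stratum.

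**Analysis.** The statistical section says that "the primary analysis will be the two-way Analysis of Variance (ANOVA) with interaction". The robustness check is an aligned-rank test for the same two-way layout. Neither has a surgeon term.

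**The concern.** On a subjective five-point scale, two surgeons can score the same field differently as a matter of habit. If more than one rates, that stable difference is variance which a surgeon term would remove and which the planned model leaves in the error. Surgeons may also fall unevenly over four cells of 35 by chance and move the cell means.

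The interaction is at stake. The plan sets out to power it at 80%, and a significant interaction triggers the pairwise comparisons. It is also the planned effect with the least power, so it has the least room for extra variance.

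**Working it through.** **Inputs from the statistical section.** Cell means at 10 / 15 mm Hg: moderate 2.5 / 4.0, deep 4.3 / 4.8. Common SD 1.1, alpha 0.05, power target 80%. Stated minimum 27 per cell (108); planned 35 per cell (140).

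**Input the documents do not give.** Between-surgeon variance. Every figure that uses it below is an assumption shown as a range.

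**Contrasts.**
- Block: (4.3 + 4.8)/2 − (2.5 + 4.0)/2 = 1.3
- Pressure: (4.0 + 4.8)/2 − (2.5 + 4.3)/2 = 1.0
- Interaction: (4.8 − 4.3) − (4.0 − 2.5) = −1.0

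**Formula.** F test with 1 and 4n − 4 degrees of freedom and noncentrality n·d²/(k·SD²), where k = 1 for a main effect and k = 4 for the interaction. Errors are taken as normal, as in the plan.

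**Step 1: the plan's own figure.**

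| n per cell | Block | Pressure | Interaction |
|---|---|---|---|
| 27 | >99.9% | 99.7% | 64.8% |
| 35 | >99.9% | >99.9% | 76.1% |

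For the interaction at 35 per cell, the noncentrality is 35 × 1/(4 × 1.21) = 7.23. The stated minimum of 108 is not reproduced for the interaction: 80% needs 39 per cell, 156 in total. That is a separate matter; here it only sets the baseline.

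**Step 2a: SD 1.1 already contains between-surgeon SD s.** The residual SD after adjustment is √(1.21 − s²).

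| Assumed s | Residual SD | Interaction power, 35 per cell |
|---|---|---|
| 0 (one surgeon) | 1.10 | 76.1% |
| 0.3 | 1.06 | 79.3% |
| 0.5 | 0.98 | 85.0% |
| 0.6 | 0.92 | 89.0% |

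Charging one or two degrees of freedom for surgeon changes these by less than 0.01 percentage points. The last row is a strong assumption: 0.36/1.21, about 30% of all variance, would be rater variance.

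**Step 2b: 1.1 is a within-surgeon SD and surgeon is ignored.** The error SD is √(1.21 + s²), which is 1.14, 1.21 or 1.25 for the same s. Interaction power falls to 73.1%, 68.1% or 65.0%. The smaller main effect (pressure) keeps at least 99.7%.

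**Step 3: two surgeons, cases split evenly, within-surgeon SD 1.1, 35 per cell, 10,000 simulated trials per setting.**

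| Difference between surgeons | Interaction power, unadjusted | Adjusted | Type I error, unadjusted (interaction / block) |
|---|---|---|---|
| 0.5 points | 73.6% | 75.2% | 5.4% / 5.2% |
| 1.0 point | 68.3% | 75.9% | 4.7% / 4.8% |

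**Step 4: chance imbalance in the same setting.** With difference D and half the cases each, the SD of the chance shift is D·√(0.25 × 2/70) for a main effect and D·√(0.25 × 4/35) for the interaction.
- D = 0.5: 0.04 and 0.08 points
- D = 1.0: 0.08 and 0.17 points

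These compare with planned effects of 1.3, 1.0 and 1.0.

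**The case against.** The strongest reply is that this may be a single-surgeon trial. The plural sentence on ratings concerns the 30-minute scores, the plurals in section 2.3 and item V are general blinding statements, and the primary rating is defined in the singular. Accrual rests on one surgeon's lists: 15 a month for 9 months is 135, close to the 140 to be randomized. This stands. A reader might infer from the plurals that several surgeons will rate, but the documents do not establish it. They do not exclude it either, and that gap is the point.

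Second, the size is assumed. No between-surgeon variance is given, and whether the 1.1 taken from a cited study's figure contains rater variance cannot be checked. This also stands, and the gain may be small. The plan also anchors every scale level in Table 1, blinds the surgeon, and raised the sample from 108 to 140 in case variances were larger. These measures help, but none of them takes a stable rater difference out of the error term.

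Third, a reader might infer that the primary comparison is biased or that deep versus moderate block is at risk. The working does not support that: randomization keeps the estimates unbiased on average, type I error stays near 5%, and the main effects keep their power.

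Two further extensions do not follow. The surgeon's option to request rescue at a rating of 3 does not affect the primary outcome, which precedes any rescue. The rater argument also gives no reason to add surgeon to the analyses of extubation or discharge time and pain medication, which are not surgeon ratings.

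**Conclusion.** The concern holds conditionally and is minor. The number of surgeons giving the first rating is unstated, and neither the primary model nor its rank check says what happens if there is more than one. In that case the loss is one of precision, and it matters in practice only for the interaction, which is already below the plan's 80% target.

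The gain from adjustment runs from zero (one surgeon), through 1 to 2 percentage points (two surgeons 0.5 points apart) and about 8 points (1.0 point apart), to about 13 points if 1.1 contains a between-surgeon SD of 0.6. All non-zero figures rest on assumed rater variance, the planned cell means and normal errors. The test of deep versus moderate block is not threatened under the planned means.

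**What to change.** State in section 2.5 how many surgeons will give the first rating, and record the rating surgeon for each case.

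- **If more than one rates:** prespecify surgeon as an additive fixed factor in the primary two-way ANOVA of the first rating, and align for surgeon in the aligned-rank check so that the two analyses match. Fix this before outcome data are seen; a term added afterwards would be open to challenge.
- **If one surgeon gives all ratings:** say so, and limit the conclusion to that operator. The background itself asks whether surgeons can tell moderate from deep block, so one rater's answer should not be presented as general.

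The cost is one recorded variable, a sentence or two in the analysis section, and one degree of freedom per extra surgeon out of 136 for error at 35 per cell. Sample size, randomization and clinical procedures do not change.

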Secondary outcomes will be time to extubation or discharge, and total pain medication requirements. The same two-way analysis as described for surgeon satisfaction will be used for each of these endpoints. Residuals will be examined and need for a modest transformation or rank-based methods considered. Moderate and deep NMB will also be compared with respect to the proportion of cases randomized to low insufflation pressure that were completed at low pressure. The chi-square test of proportions will be used for that analysis.

Sample size – Sample size estimates are based surgeon satisfaction rating as this is the primary outcome. Figure 3 of Martini et al.⁶ gives the frequency distribution of the surgeon satisfaction score under moderate and deep block. Scores for the moderate block have the greatest variability and so for sample size purpose the proportions from Fig. 3 were used to estimate the standard deviation of the surgeon satisfaction score ($\sigma = 1.1$). Based on literature and clinical judgement we powered the study to have at least 80% power to detect statistically significant ($p < 0.05$) effects for the main effects and interaction term in a two-way analysis of variance assuming the following configuration of mean satisfaction scores and a common standard deviation of 1.1.

		Pressure	
		10mmHG	15mmHG
Block	Moderate	2.5	4.0
	Deep	4.3	4.8

Power curves for each of the ANOVA effects are displayed in Figure 1. The required minimum sample size is 108 subjects, allocated 27 per treatment combination. To guard against potential optimism in these calculations (actual variances could be larger or effects smaller) we intend to recruit 35 subject per treatment combination for a total sample size of 140.

Power calculations were carried out using GLMPOWER procedure in SAS v 9.3.

Specific Drug Supply Requirements:

The anesthetic agents utilized in this study (including rocuronium) are routinely used for this type of surgery and are acceptable patient costs. However, sugammadex just received FDA approval in December 2015 and is not currently used for NMB reversal at our institution. We will receive adequate supplies of sugammadex from Merck &Co. so that there will be no charge to the patients for this medication.

2.11 References:

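### Randomization is stratified by BMI, but no planned analysis uses the stratum; if BMI predicts the outcome, a small and almost costless gain in precision is lost (minor).

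*Combined protocol and SAP*

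**What the plan says.** Section 2.5, item IV (Randomization) allocates patients to four block-by-pressure groups and balances BMI across them: "Randomization will be stratified for the four groups so that obese patients with BMI of 35 to 45 and those with a BMI" above 45 "are equally distributed between the groups". Item VIII.b of the same section describes the allocation differently. There, "the intra-abdominal pressure is either 10 or 15 mm Hg per a second randomization list", and nothing says whether that list is stratified by BMI.

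The section Statistical Analysis and Sample Size Justification names four analyses:

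- Primary: "The experimental layout is a randomized two-factor design so the primary analysis will be the two-way Analysis of Variance (ANOVA) with interaction".
- Check on the primary: "the robustness of the results will be checked against an aligned-rank test for the two-way layout".
- Secondary outcomes (time to extubation or discharge, and pain medication): "The same two-way analysis as described for surgeon satisfaction will be used for each of these endpoints".
- Completion at low pressure, moderate against deep block: "The chi-square test of proportions will be used for that analysis".

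None includes BMI or the stratum, and no other analysis in the document does.

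**The concern.** Balancing a prognostic factor across groups makes the treatment contrasts more precise. A model without that factor leaves the between-stratum variance in the residual, so the standard errors, confidence intervals and p-values do not show the gain. The estimates stay unbiased, and the tests err on the conservative side.

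Three places could benefit:

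- the interaction, which the plan powers for and which triggers the pairwise comparisons;
- a block effect well below the planned 1.3 points, a case the sample size text allows for when it says effects could be smaller;
- low-pressure completion, which rests on about 70 patients.

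**Working it through.** **Inputs from the sample size text.** Cell means are 2.5 and 4.0 (moderate block at 10 and 15 mm Hg) and 4.3 and 4.8 (deep block). SD is 1.1, with 35 per cell (140 in all) and 0.05 for significance.

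- Block effect: (4.3 + 4.8)/2 − (2.5 + 4.0)/2 = 1.3.
- Pressure effect: (4.0 + 4.8)/2 − (2.5 + 4.3)/2 = 1.0.
- Interaction: (4.0 − 2.5) − (4.8 − 4.3) = 1.0.

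**Assumptions, not in the documents.** BMI stratum explains a share R² of within-cell variance, and the two strata are equally common.

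**The plan's own figure.** The standard error of the interaction contrast is 2 × 1.1/√n. At n = 35 it is 0.372, so the noncentrality is (1.0/0.372)² = 7.23. With F(1, 136) the power is 76.1%. At the plan's minimum of 27 per cell it is 64.8%, so the claimed 80% for the interaction is not reproduced. That is a separate matter. Here it shows only that the interaction is the tight test. Power at 35 per cell exceeds 99.9% for both main effects.

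**Four-group stratified scheme, normal scores.** With BMI in the model, the residual variance is 1.21 × (1 − R²) on 135 degrees of freedom, and power comes from the noncentral F. Without BMI, the contrast has that same variance, but the residual sum of squares also carries the stratum difference. Scaled by 1.21 × (1 − R²), it is noncentral chi-square with 136 degrees of freedom and noncentrality 140 R²/(1 − R²).

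| R² | Interaction power, no BMI | With BMI | True size of unadjusted test |
|---|---|---|---|
| 0 | 76.1% | 76.1% | 0.050 |
| 0.02 | 76.3% | 76.9% | 0.048 |
| 0.05 | 76.6% | 78.2% | 0.044 |
| 0.10 | 77.2% | 80.4% | 0.039 |
| 0.15 | 77.8% | 82.5% | 0.033 |

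**Pressure from a separate list that ignores BMI** (one reading of item VIII.b; simulation, 100,000 runs per row). Power goes from 76.3% to 78.2% at R² = 0.05 and from 76.0% to 80.0% at R² = 0.10. At R² = 0 it goes from 76.2% to 75.8%. In the 1-5 simulation of this scheme the unadjusted interaction test has size 0.050.

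**Scores confined to 1-5.** The endpoint is bounded: "The satisfaction level will be rated with a five-point ordinal scale ranging from 1 (extremely poor) to 5 (optimal conditions". A cell with mean 4.8 cannot have an SD above √(0.2 × 3.8) = 0.87, so the normal model with SD 1.1 cannot hold there. Simulated scores were rounded and clipped to 1-5:

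| Scheme and means | R² = 0.05 | R² = 0.10 |
|---|---|---|
| Four-group, latent means as planned | 90.5% to 91.2% | 91.1% to 92.5% |
| Four-group, observed means held at plan | 92.3% to 92.9% | 93.0% to 94.0% |
| Separate list, latent means as planned | 89.9% to 91.0% | 89.9% to 92.1% |
| Separate list, observed means held at plan | 91.9% to 92.7% | 91.8% to 93.5% |

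The gain is 0.6 to 1.4 points under the four-group scheme and 0.8 to 2.2 points under a separate list. In the null runs (observed means 3.0, 4.0, 3.5, 4.5) the adjusted interaction test had size 0.049 to 0.050 under both schemes. If the block effect is 0.5 instead of 1.3, its power on this scale goes from 86.5% to 87.5% (R² = 0.05) or from 86.9% to 88.8% (R² = 0.10), four-group scheme.

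**Low-pressure completion** (assumed 40% against 70%, 35 per arm, four-group scheme; simulation):

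| Assumed gap in completion between BMI strata | Chi-square | Mantel-Haenszel |
|---|---|---|
| 0 points | 70.6% | 70.5% |
| 10 points | 70.8% | 71.3% |
| 20 points | 71.0% | 73.5% |
| 30 points | 71.6% | 77.1% |

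A separate list gives similar figures at gaps of 20 and 30 points: chi-square 70.9% and 71.2%, Mantel-Haenszel 73.8% and 76.6%.

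**The case against.** The unadjusted ANOVA is a valid, pre-specified analysis. The single primary hypothesis concerns block depth, and at the planning means its power cannot usefully be improved. The omission errs only on the conservative side. The benefit depends on an R² that the documents do not supply: at 0.02 the interaction gains about 0.6 points, and at zero nothing. The larger gains come from a normal model that the 1-5 scale rules out in at least one cell. The completion rates and BMI gaps are assumed as well, and at a 10-point gap the gain is only about 0.5 points. The reading with an unstratified second list is one that the protocol does not spell out.

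All of this stands, and it is why the point is minor and conditional. It does not give a reason to leave the term out. The protocol judged BMI important enough to balance, the data are already in hand, and the loss if BMI proves unrelated to the score is negligible. The evidence that the adjusted test keeps its level is limited to the score model. For the Mantel-Haenszel test, a check under the four-group scheme gave a size of 0.044 to 0.050. The other secondary models were not checked.

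**Conclusion.** The concern holds as a minor one: the trial randomizes by BMI stratum and analyses without it. Validity is not affected. If BMI explains 5% to 10% of within-cell variance, adjustment adds about 1.6 to 3.2 points of interaction power under the plan's normal model with the four-group scheme (78.2 − 76.6 and 80.4 − 77.2), and about 1 point on the bounded scale. Low-pressure completion could gain about 2.5 to 5.5 points, but only if completion differs between BMI strata by 20 to 30 points. At the planning means the block test is unaffected in practice. R², the even split of strata and the completion rates are all assumptions; if BMI is not prognostic, there is no gain.

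**What to change.** Before the data are seen, pre-specify the primary model as score = block + pressure + block × pressure + BMI stratum (35 to 45 against above 45), and carry the same term into the secondary two-way models. Replace the plain chi-square for low-pressure completion with a Mantel-Haenszel test stratified by BMI. Adding the term to the aligned-rank check is optional. Fixing this in advance keeps the choice of covariate from depending on the results.

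The cost is one added term, 1 of 136 residual degrees of freedom, and one changed test. No new data are needed, because BMI is both an inclusion criterion and the stratification factor. If BMI is unrelated to the score, interaction power falls by less than 0.01 point under the four-group scheme and by about 0.4 points at most under a separate unstratified list. The two descriptions of the allocation should be reconciled, but this change need not wait for that: in the simulations the adjusted interaction test kept its level under both.

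### Pressure-specific deep-versus-moderate comparisons of the primary rating depend on a significant interaction, whose power on the plan's stated inputs is 65% at 27 and 76% at 35 per cell, not the stated 80% or more

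*Combined protocol and SAP*

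**What the plan says.** All references are to the combined protocol and SAP.

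- **Design.** Section 2.5, item IV, randomizes patients to four groups: moderate or deep block, each at 10 or 15 mm Hg.
- **Outcome.** Section 2.5, item VIII.a, makes the first surgeon rating the primary outcome, on a "five-point ordinal scale ranging from 1 (extremely poor) to 5 (optimal conditions").
- **Analysis.** Statistical Analysis and Sample Size Justification makes a two-way ANOVA with interaction the primary analysis. Its one provision for cell-level results on the rating is: "A statistically significant interaction will be followed by pairwise comparisons to identify and estimate treatment combination differences". It acknowledges that "The standard ANOVA assumes a normally distributed outcomes with homogeneous variances" and adds an aligned-rank check.
- **Low pressure.** The same section compares the blocks by chi-square on "the proportion of cases randomized to low insufflation pressure that were completed at low pressure". This does not depend on the interaction, but it is a different outcome.
- **Sample size.** The study is said to have at least 80% power for "effects for the main effects and interaction term in a two-way analysis of variance". That calculation was made "assuming the following configuration of mean satisfaction scores and a common standard deviation of 1.1". The means are 2.5 and 4.0 (moderate, 10 and 15 mm Hg) and 4.3 and 4.8 (deep). The stated minimum is 27 per cell (108), raised to 35 (140) because "actual variances could be larger or effects smaller".

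**The concern.** The plan expects the benefit of deep block to depend on pressure, and it randomizes pressure. Yet it commits to comparing the blocks within each pressure only after a significant interaction. An interaction is the least precisely estimated term in a 2x2 design, and a non-significant result does not show that the effects are equal. When the test misses, the planned report of the block effect is an average of 1.3 points, 0.5 away from each of the two effects the plan assumes. Any pressure-specific comparison would then be post hoc.

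The plan appears to cover this by claiming at least 80% power for the interaction at 27 per cell, with 35 per cell as a margin. That claim does not follow from the stated inputs, and one of those inputs cannot occur on the scale used.

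**Working it through.** **Inputs (sample-size paragraph).** Means 2.5, 4.0, 4.3, 4.8; SD 1.1; alpha 0.05; n = 27 or 35 per cell. The power curves are in a figure not available here, so the check uses the stated inputs.

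**1. Planned effects.**
- Block at 10 mm Hg: 4.3 - 2.5 = 1.8. Block at 15 mm Hg: 4.8 - 4.0 = 0.8.
- Average block effect: (1.8 + 0.8)/2 = 1.3.
- Interaction: 1.8 - 0.8 = 1.0.

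**2. The plan's own power figure.** Noncentral F with 1 and 4(n-1) df; noncentrality = 1.0² / (sum of the four cell variances / n). With SD 1.1 throughout, the variances sum to 4 × 1.21 = 4.84.

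| n per cell | Noncentrality | Interaction power |
|---|---|---|
| 27 | 27/4.84 = 5.58 | 64.8% |
| 35 | 35/4.84 = 7.23 | 76.1% |
| 38 | 38/4.84 = 7.85 | 79.5% |
| 39 | 39/4.84 = 8.06 | 80.5% |

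The stated 27 per cell is not reproduced. A one-sided test does not rescue it (75.9% at 27; 31 per cell needed). The main effects are amply powered at 27: block over 99.9%, pressure 99.7%.

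**3. Is SD 1.1 possible?** On a 1-5 scale the largest SD at mean m is √((5-m)(m-1)). At 4.8 this is √(0.2 × 3.8) = 0.87. The smallest SD for whole-number scores at 4.8 is √(0.2 × 0.8) = 0.40. The maxima for means 2.5, 4.0 and 4.3 are 1.94, 1.73 and 1.52, so only the deep/15 cell is affected. A common SD is possible only between 0.50 (the minimum at mean 2.5) and 0.87.

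**4. Interaction power with attainable SDs, planned means, 35 per cell.**

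| SDs | Sum of variances | Power | Comparisons withheld |
|---|---|---|---|
| 1.1 in three cells, 0.87 in deep/15 | 3.63 + 0.76 = 4.39 | 80.1% | 20% |
| 1.1 in three cells, 0.40 in deep/15 | 3.63 + 0.16 = 3.79 | 85.5% | 15% |
| Common 0.87 | 4 × 0.76 = 3.04 | 92.1% | 8% |

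A smaller common SD gives higher power. At 27 per cell the three rows give 69.0%, 75.3% and 83.9%.

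**5. Smaller effects.** At three quarters of the planned differences the interaction is 0.75. The deep/15 mean becomes 4.225, where SD 1.1 is attainable (maximum 1.58). Power at 35 per cell is then 51.7%.

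**6. What the condition costs on the stated inputs (SD 1.1 throughout, unadjusted, 200,000 simulated trials).** The chance of reporting a significant 15 mm Hg difference falls from 86% to 62%, and at 10 mm Hg from over 99% to 76%. These figures carry the impossible SD, so they describe the plan's own arithmetic rather than a forecast.

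**7. Side note: intervals.** If the comparisons used the ANOVA's pooled error, with SD 1.1 in three cells and 0.40-0.87 in deep/15, 95% intervals would cover 92-94% at 10 mm Hg and 96-98% at 15 mm Hg. Welch intervals cover about 95% at both.

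**The case against.** Testing the interaction first and following it up if significant is a conventional factorial strategy, and the plan does not say that comparisons are otherwise forbidden. The fitted model estimates the interaction and all four cell means whatever the p-values: an average effect of 1.3 and an interaction of 1.0 return 1.8 and 0.8 exactly. This stands. A reader might infer that the pressure-specific information is lost. It is not; what is lost is the prespecified commitment to present and test it.

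The primary hypothesis in section 2.1.1 concerns deep versus moderate block overall, and the low-pressure hypothesis has its own chi-square test. Both points stand, and they limit the weight of the concern.

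The SD of 1.1 was chosen cautiously, because "Scores for the moderate block have the greatest variability". That also stands: the impossible value makes the power calculation conservative. A reader might therefore take 76% as the trial's real interaction power, or 24% as the real rate of withheld comparisons. The documents do not support that, because with the planned means the SD behind those figures cannot occur in one cell. Equally, caution in the SD does not make the stated 80% at 27 per cell follow from the stated inputs.

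The interval distortion in step 7 is modest, requires unequal variances, and depends on an estimator the plan does not name. It is not a defect in itself.

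**Conclusion.** The concern holds in a limited form.

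- **Conditional comparisons.** With the planned means, 35 per cell and the attainable SDs examined, the interaction test would withhold the planned pressure-specific comparisons in roughly 8-20% of trials: 15-20% with SD 1.1 in the other three cells, 8% or less with a common SD of 0.87 or below. If effects are smaller, which the plan itself allows, the share rises: about 48% at three-quarter effects and SD 1.1.
- **Power statement.** On the stated inputs, interaction power is 65% at 27 and 76% at 35 per cell, against a claim of at least 80%. For this term the increase to 35 is not a safety margin on those inputs. They also include an SD that is unattainable at mean 4.8.

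A reader might infer that the primary test is compromised or the trial too small. Neither follows. The block main effect has over 99.9% power even at 27 per cell, and with attainable SDs the interaction reaches about 80% or more at 35.

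The result rests on the planned means and on 1.1 as the largest cell SD. The source of 1.1, a figure in a cited study, could not be checked.

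**What to change.** 1. **Analysis paragraph.** Prespecify deep versus moderate at 10 mm Hg and at 15 mm Hg on the primary rating as secondary contrasts. Report both with confidence intervals whatever the interaction p-value, using Welch or heteroscedasticity-consistent standard errors and Holm-adjusted p-values. Keep the two-way ANOVA, its interaction test, the aligned-rank check and the chi-square test.
2. **Sample-size paragraph.** Either restate interaction power as 65% at 27 and 76% at 35 per cell on the stated inputs, or recompute it with SDs attainable on the 1-5 scale. Do not enlarge the trial.

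**Cost.** Wording only; no extra patients or data. With SD 1.1 in three cells, the 95% half-width at 10 mm Hg becomes 1.995 × √(2.42/35) = 0.52, instead of 0.46-0.50 with pooled error. At 15 mm Hg it narrows to 0.40-0.47. If simultaneous intervals are wanted, the 97.5% level gives 0.60 at 10 mm Hg. At the planned means, Holm-adjusted Welch tests have over 99% power at 10 mm Hg and 89-99% at 15 mm Hg. The other cost is a less favourable stated power if the original inputs are kept.
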